## **10.6** Pregnancy Reporting

All pregnancies within the trial should be reported using the Pregnancy Reporting Form within 24 hours of notification. The Chief Investigator and the TMG will be informed, so that a discussion can take place regarding the participant's continuation in the study. Any such discussions will be documented, and recommendations for continuation or discontinuation in the study will be made according to clinical judgement.

Pregnancy is not considered an AE unless a negative or consequential outcome is recorded for the mother or child/foetus. If the outcome meets the criteria for seriousness, this would be considered an SAE. Any participant who becomes pregnant whilst taking IMP will be asked to consent to follow up of the pregnancy, irrespective of any treatment withdrawal or changes. Follow up will be recorded on the pregnancy follow-up form. Pregnancy reporting requirements for partners of participants are provided in the IMP-specific appendices.

The DMEC and the Programme Steering Committee (PSC) will be advised at each meeting, of any pregnancies reported since their previous meeting.

## **10.7 CTRU responsibilities**

CTRU will assess all SARs for expectedness in collaboration with the CI. An unexpected adverse reaction is one which is not previously reported in the Reference Safety Information (RSI) used in the study, or one that is more frequent or more severe than reported in the RSI. If a SAR is assessed as 'unexpected', it is classified as a SUSAR.

The RSI to be used in the study will be section 4.8 of the SmPC for the relevant IMP in the version which has been submitted to and approved by the MHRA for this trial.

The Sponsor has delegated CTRU responsibility for the reporting of SUSARs and other SARs to the regulatory authorities and the research ethics committee as appropriate. CTRU will also keep all investigators informed of any safety issues that arise during the course of the study. CTRU will report all SAEs to the Sponsor as documented in the delegation of duties agreement.

The DMEC and TMG will also receive information on all AEs and SAEs, at a frequency agreed with each committee and documented in the appropriate charter/terms of reference.

#### 10.8 SUSARs

The CTRU will be responsible for reporting SUSARs to the MHRA and REC in line with regulatory requirements. Fatal or life-threatening SUSARs will be reported no later than 7 calendar days of CTRU being aware of the event. All other SUSARs will be reported no later than 15 calendar days of CTRU being aware of the event. Each site will be informed of SUSARs occurring across the study.

## **11. Statistics**

#### **11.1 Statistical Analysis**

There are six possible conclusions for a given candidate drug:

1. Potential effectiveness of a candidate drug: the predictive probability of a reduction in NFL levels at 18 to 24 weeks is >97.5%

- 2. Futility: the predictive probability of reaching a mean reduction in NFL levels of 0.15 log10 units or more is <1%
- 3. Non-inferiority compared with current reference drug: the posterior probability of being inferior to the reference drug by 0.10 log10 units or more is <=2.5%.
- 4. Superiority over current reference drug: the posterior probability of being superior to the reference drug by 0.10 log10 units or more is >=97.5%.
- 5. No established non-inferiority compared with the current reference drug: the posterior probability of being inferior to the reference drug by 0.10 log10 units or more is >2.5%.
- No established superiority compared with the current reference drug: the posterior probability of being superior to the reference drug by 0.10 log10 units or more is <97.5%.

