To achieve >80% power for both non-inferiority and superiority analyses, the target sample size is set at 80 patients per candidate drug who will be randomised and followed-up until 18 to 24 weeks. This sample size will result in >80% power to declare non-inferiority to the concurrently randomised reference drug based on a non-inferiority margin of 0.10 log10 units or to declare superiority over the reference drug provided that the true mean reduction in NFL levels associated with the candidate drug is 0.10 log10 units greater than the reduction seen with the reference drug. Non-inferiority will be declared if the Bayesian posterior probability of having a decrease from baseline at 18 to 24 weeks of follow-up that is 0.10 log10 units smaller than the decrease of NFL levels of the reference drug is 2.5% or less. If non-inferiority is reached, we will test for superiority. Superiority will be declared if the posterior probability of having a decrease from baseline larger than the competitor drug is 97.5% or more. To ensure sufficient power of superiority analyses, we will estimate the predictive probability to detect superiority of a candidate drug given the observed data over the reference drug (analogous to conditional power) when 50 randomised patients per arm have reached 18 weeks of follow-up. If the predictive probability is above 60% but below 80%, we will consider increasing the target sample size to reach a predictive probability of 80%. If the predictive probability is below 60% or above 80%, we will adhere to a target sample size of 80 patients per candidate drug. Figure 1 (above) illustrates corresponding analyses and adaptations at trial arm level.

We aim to recruit approximately 700 people with ALS from 11 centres over 43 months and screen between 9 and 20 candidate drugs, depending on the number of drugs that are retained after futility analyses.

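### Sections 11.1 and 11.2 set different rules for superiority over the reference drug, and under the Section 11.1 rule the stated power of over 80% is about 2.5%

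*Protocol*

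**What the plan says.** Section 11.1 of the protocol lists six possible conclusions for a candidate drug. Conclusion 4 reads: "Superiority over current reference drug: the posterior probability of being superior to the reference drug by 0.10 log10 units or more is >=97.5" per cent. Conclusion 6, its complement, repeats the threshold: superiority is not established if "the posterior probability of being superior to the reference drug by 0.10 log10 units or more is <97.5" per cent.

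Section 11.2 gives a different rule: "Superiority will be declared if the posterior probability of having a decrease from baseline larger than the competitor drug is 97.5% or more". No minimum difference is attached, so any advantage above zero counts. The same paragraph sets the size of the pairwise comparison: "To achieve >80% power for both non-inferiority and superiority analyses", "the target sample size is set at 80 patients per candidate drug". The superiority power is claimed "provided that the true mean reduction in NFL levels associated with the candidate drug is 0.10 log10 units greater" than the reduction on the reference drug.

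Later in Section 11.1, under the primary outcome analysis, demonstrated superiority is one of two grounds for considering a candidate as the new reference drug. That evaluation is referred back to the criteria in the protocol, without saying which of the two rules is meant.

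**The concern.** The two rules test different hypotheses: an advantage of at least 0.10 log10 units, or an advantage above zero. Both stand in the current text, and the 0.10 threshold appears in two of the six conclusions, so it does not look like an isolated slip. The non-inferiority rule, by contrast, agrees between the sections (margin 0.10, posterior probability of 2.5% or less).

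The power statement makes the conflict more than a matter of wording. Power is quoted at a true difference equal to the Section 11.1 threshold, and no sample size gives good power there.

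Three uses of superiority are affected:

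- The choice of a new reference drug, where the same data could be superior under one section and not under the other.
- The check at 50 patients per arm in Section 11.2, where a predictive probability of superiority between 60% and 80% may lead to a larger sample. Read in place, it follows the Section 11.2 rule, which conflicts with the formal conclusions in Section 11.1.
- The prioritisation of drugs for Phase III, where a finding of superiority counts in a drug's favour.

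**Working it through.** **Inputs**

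- 80 patients per arm, true difference 0.10 log10 units, posterior threshold 97.5% (Section 11.2).
- SD at one time point 0.35 log10 units (Section 11.2).
- Correlation between baseline and follow-up 0.80. Section 11.2 gives this for the futility analyses; using it for the pairwise analysis is an assumption. The same section reports at least 0.85 in the source dataset.
- Minimally informative priors (Section 11.1), so a 97.5% posterior threshold behaves like a one-sided 2.5% test with critical value 1.96.
- All 80 patients per arm are taken as evaluable.

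**Step 1. Standard error of the difference between arms (one baseline, one follow-up value)**

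- Change score: SD = 0.35 × √(2 × (1 − 0.80)) = 0.2214; SE = 0.2214 × √(2/80) = 0.0350.
- ANCOVA: SD = 0.35 × √(1 − 0.80²) = 0.21; SE = 0.21 × √(2/80) = 0.0332.

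**Step 2. Reproducing the stated power with the Section 11.2 rule (difference above 0)**

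Power = Φ(0.10/SE − 1.96).

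- Change score: Φ(0.10/0.0350 − 1.96) = 81.5%; 77 per arm would give 80%.
- ANCOVA: Φ(0.10/0.0332 − 1.96) = 85.4%; 70 per arm would give 80%. A simulation of 20,000 trials gave 84.4%.
- Correlation 0.85: 91% (change score) to 93% (ANCOVA).
- Two baseline and two follow-up values, correlation 0.80 between every pair: SE 0.0241 (ANCOVA) to 0.0247 (change score), power about 98% to 99%.

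The claim of more than 80% holds under this rule in every one of these cases.

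**Step 3. The Section 11.1 rule (difference of at least 0.10)**

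Power = Φ((true difference − 0.10)/SE − 1.96).

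At a true difference of 0.10 the first term is zero, so power = Φ(−1.96) = 2.5%. The SE drops out, so sample size, SD and correlation do not matter. The simulation also gave 2.5%.

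**Step 4. What the Section 11.1 rule would need with 80 per arm**

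True difference for 80% power = 0.10 + (1.96 + 0.84) × SE.

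| Data used (correlation 0.80) | SE | True difference needed |
|---|---|---|
| One baseline, one follow-up, change score | 0.0350 | 0.198 |
| One baseline, one follow-up, ANCOVA | 0.0332 | 0.193 |
| Two baseline, two follow-up, change score | 0.0247 | 0.169 |
| Two baseline, two follow-up, ANCOVA | 0.0241 | 0.167 |

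At a true difference of 0.15, power with single measures is Φ(0.05/0.0350 − 1.96) = 30% to Φ(0.05/0.0332 − 1.96) = 33%.

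**Step 5. How often the rules disagree**

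With SE 0.0350, Section 11.2 declares superiority from an observed difference of 1.96 × 0.0350 = 0.069. Section 11.1 does so only from 0.10 + 0.069 = 0.169. Results between the two are superior under one section and not under the other. At the planned true difference that is 81.5% − 2.5% = 79% of trials.

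**Step 6. The check at 50 patients per arm**

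The final cut-off differs by 0.10 between the rules. With minimally informative priors the predicted final difference is centred on the interim one. The range of interim differences that gives a predictive probability of 60% to 80% therefore also moves up by 0.10 log10 units when Section 11.1 is used.

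**The case against.** Several points can fairly be made for the protocol.

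- Superiority under Section 11.1 is not impossible. The trial looks for large effects, and the first reference drug need only show some reduction, so a candidate could truly be 0.17 to 0.20 log10 units better. This stands: the rule is out of reach at the planned difference of 0.10, not at every difference.
- The agreement of 81.5% to 85.4% with the stated figure does not show how 80 per arm was derived. The model in Section 11.1 uses two baseline and two follow-up values, which gives about 98%, and the correlation is carried over from the futility analyses. This also stands, but the 2.5% depends on neither point.
- The threshold of 0.10 may be deliberate, as a criterion of relevant superiority that mirrors the non-inferiority margin. That is possible, and the simulations behind the cut-offs are not shown. The power statement would then be wrong instead, so the text still needs correcting.
- The consequences are limited. Superiority leads only to consideration by the committees, non-inferiority is a separate route to reference status, and Phase III candidacy does not require superiority. Futility decisions are untouched. This limits the damage, but superiority remains one of six formal conclusions on the primary outcome, with its own power claim and its own sample-size adaptation.

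Leaving the matter to the SAP is no answer. The protocol itself fixes both rules and refers the choice of reference drug back to its own criteria.

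**Conclusion.** The concern holds: the text is wrong as written and must be fixed. The protocol contains two incompatible superiority rules, and its claim of more than 80% power is true only for the one in Section 11.2. Under the Section 11.1 rule, power at the stated difference of 0.10 log10 units is 2.5%. That figure rests only on the minimally informative prior and on the true difference equalling the threshold. The figures for the Section 11.2 rule (81.5% to 85.4% with single measures, about 98% with two baseline and two follow-up values) and the 0.17 to 0.20 needed under Section 11.1 also assume SD 0.35, correlation 0.80 and 80 evaluable patients per arm. The non-inferiority gate changes nothing, because a result that meets either superiority rule already meets non-inferiority.

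**What to change.** Reword conclusions 4 and 6 in Section 11.1 to agree with Section 11.2:

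- Conclusion 4: superiority is established if the posterior probability that the candidate's reduction in NFL exceeds the reference drug's (difference above zero) is at least 97.5%.
- Conclusion 6: superiority is not established if that probability is below 97.5%.

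Keep 0.10 log10 units only as the non-inferiority margin and as the true difference at which power is quoted. State that the predictive probability at 50 patients per arm uses the same rule, and carry the definition into the SAP. Confirm that the design simulations cited in Section 11.1 used it.

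The cost is wording in one section and the matching SAP definition. The sample size and the stated power stay as they are, and no extra patients are needed. If the sponsor does intend the 0.10 threshold, Section 11.2 must change instead: the power has to be restated at a larger true difference (about 0.17 to 0.20 log10 units for 80% power with 80 per arm) and the sample size reconsidered.

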#### Primary outcome analysis

We will use a Bayesian linear model with minimally informative priors that allows for repeated NFL levels assessed at 18 and 24 weeks, with inclusion of baseline NFL levels assessed at the screening visit at -2 weeks and before randomization at week 0. NFL levels originally measured in pg/mL will be log10 transformed to achieve more symmetrical distributions. The primary outcome analysis will follow the intention-to-treat principle, where all patients will be analysed as randomised.

A multivariable Bayesian prediction model that incorporates baseline characteristics and NFL levels pre-randomization and intermediate NFL levels ascertained at 12 weeks as covariates will be used to estimate predictive probabilities of futility and potential effectiveness based on all patients randomised to a trial arm at the time of an interim analysis despite incomplete follow-up. The model can account for all additional data that will accumulate until all patients have completed final follow-up, and appropriately incorporate all sources of uncertainty. Arm-specific Bayesian predictive probabilities for early identification of drugs that are unlikely to be associated with a relevant decrease in NFL levels from baseline will be estimated, declaring futility as described above after at least 16 patients (in case of futility analysis 1) and 20 patients (in case of futility analysis 2) have reached 18 weeks of follow-up. If a trial arm is declared futile, the DMEC will make a recommendation to the TMG who can decide to drop the drug from the trial. A previously dropped candidate drug may re-enter the trial at a higher dose if considered clinically justifiable. The cut-offs used to declare futility, potential effectiveness, non-inferiority or superiority, and decisions on timing and frequency of analyses are based on extensive simulations. A total of 2000 trials were simulated under various scenarios, each trial using 5000 iterations after a burn-in period of 1000 iterations.

If a concurrently randomised candidate drug was not declared futile based on arm-specific Bayesian predictive probabilities obtained in futility analyses 1 and 2, we will estimate pairwise between-group mean differences in NFL levels at 18 to 24 weeks with 95% credible intervals and Bayesian posterior probabilities of non-inferiority, and, if reached, superiority to the reference drug after 80 patients per arm reached 24 weeks of follow-up. Drugs that were dropped due to futility after futility analysis 1 or 2 will not be included in non-inferiority or superiority analyses.

Irrespective of which conclusion was reached for a drug, we will estimate arm-specific mean changes from baseline with 95% credible intervals with final posterior probabilities to reach a reduction from baseline. Using Bayesian network meta-analysis, which fully maintains

concurrently randomised comparisons, we will then rank all candidate drugs by their effectiveness in decreasing NFL levels and calculate the posterior probability that each candidate drug has the highest or lowest NFL decrease from baseline.

Candidate drugs associated with a decrease in NFL levels will become candidates for investigation in a Phase III trial, particularly if they were considered non-inferior or superior to effective reference drugs as described above. Candidate drugs that ranked lower than reference drugs but were associated with a decrease in NFL levels can be considered for investigation in a Phase III trial based on other possible advantages, such as better safety profile and/or lower costs.

The first candidate drug that is retained after futility analyses 1 and 2 and associated with >97.5% probability of a reduction in mean group NFL levels different from zero at 18 to 24 weeks after 80 patients per arm reached 24 weeks of follow-up will be considered the first reference drug. As the trial continues, patients will continue to be randomised to this reference drug as long as DMEC and/or TMG do not consider another candidate drug as reference. Figure 2 (above) illustrates potential adaptations to trial arms following the planned futility analyses for the example of three concurrently evaluated drugs.

Candidate drugs should be considered as the potential new reference drug by the DMEC and/or TMG under two scenarios:

- 1. Superiority to current reference drug: If a candidate drug has demonstrated superiority over the current reference drug, it warrants consideration as a new reference drug. This evaluation should adhere to the predefined criteria established in the protocol.
- 2. Non-inferiority to current reference drug: A candidate drug may also be considered as the new reference drug if it has been shown to be non-inferior to the current reference drug following the criteria established in the protocol. This consideration may be triggered by factors such as improved tolerability or when the DMEC believes that sufficient data have been accumulated for the current reference drug within the context of the platform trial so that a change to a new reference drug is warranted.

Further details of the primary outcome analysis will be pre-specified in the statistical analysis plan. In the event that a candidate drug has a prolonged titration phase to reach the target dose, the statistical analysis plan may be amended to account for this.

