## 7. Randomisation and enrolment

Prior to randomisation, all screening investigations will be reviewed by the local medically qualified investigator to confirm eligibility. The investigator will complete and sign the "Confirmation of Eligibility" form as documentation of this review. The investigator will be

responsible for indicating which of the treatment arms the patient is eligible for as this information will be required for randomisation. A patient must be eligible for a minimum of two treatment arms.

Once eligibility has been confirmed and baseline data recorded, the participant will be randomly allocated to one of the current treatment options for which they are eligible. A member of the local study team will perform the randomisation by accessing a web-based randomisation system provided by the Sheffield CTRU (SCRAM). Patient details (ID, age, eligibility details) will be entered and the treatment allocation will be returned. We will use probabilistic minimisation to balance site of onset (bulbar vs spinal) and groups of trial sites based on patient volume (high (Oxford, Sheffield, King's College) vs medium (Salford, University College London, Newcastle, Liverpool) vs low (Cambridge, Edinburgh, South Wales, Exeter)).

Following randomisation, all patients must be given a patient contact card. Site on-call contact details for 24-hour medical care must be added to this card, and participants advised to carry this with them at all times whilst participating in the trial. Where licenced products, 24-hour medical care will be provided via routine out of hours services i.e. trial-specific out of hours cover will not be required. Where non-licenced products, please refer to the IMP-specific appendices for more information.

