#### 11.2 Sample size

In a dataset with repeated NFL levels provided by the Clinical Research in ALS and Related Disorders for Therapeutic Development (CreATe) Consortium, the correlation between repeated measures of log10 transformed NFL levels (pg/mL), obtained within 2 to 8 months, was  $\geq 0.85$  (5). The typical standard deviation at any given measurement time point was 0.35 log10 units.

Figure 1 (above) illustrates the analyses and adaptations at trial arm level. The first futility analysis will be conducted when at least 23 randomised patients per candidate drug reached 12 weeks and at least 16 patients reached 18 weeks of follow-up, which will occur when approximately 28 patients per arm were randomised. This will result in >85% power to detect an average decrease in NFL levels from baseline of 0.15 log10 units and >80% power to declare futility of the candidate drug, assuming a correlation between baseline and follow-up of 0.80. The second futility analysis will be conducted when at least 29 randomised patients per candidate drug reached 12 weeks of follow-up and at least 20 patients reached 18 weeks of follow-up, which will occur when approximately 35 patients per arm were randomised (Figure 1). This will result in >90% power to detect an average decrease in NFL levels from baseline of 0.15 log10 units or declare futility of the candidate drug, assuming a correlation between baseline and follow-up of 0.80. A decrease in NFL levels of 0.15 log10 units, for example, corresponds to a 30% decrease in the geometric mean from 60 pg/mL at baseline to 42 pg/mL at 18 to 24 weeks of follow-up. Of note, since recruitment is accelerating at the beginning of the platform trial, the number of patients randomised will be somewhat higher when futility analyses 1 and 2 will be performed during the first phase of the platform trial.

Potential effectiveness in decreasing NFL levels will be declared if the Bayesian predictive probability of a candidate drug to reach any reduction from baseline at 18 to 24 weeks of follow-up is 97.5% or more. Futility or potential harm will be declared if the posterior predictive probability of a candidate drug to reach a reduction of at least 0.15 log10 units at 18 to 24 weeks of follow-up is 1% or less.

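### The protocol names baseline NFL as the final model's only covariate, although allocation is minimised on site of onset and site-volume group; naming both for the pairwise comparisons is a minor, nearly free gain

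*Protocol*

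**What the plan says.** Section 7 sets the allocation method: "We will use probabilistic minimisation to balance site of onset (bulbar vs spinal) and groups of trial sites based on patient volume". Onset has two levels and site volume has three (high, medium, low).

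Section 11.1 (Primary outcome analysis) gives the final model as a Bayesian linear model with minimally informative priors for log10 NFL at weeks 18 and 24, "with inclusion of baseline NFL levels assessed at the screening visit at -2 weeks and before randomization at week 0". Baseline NFL is the only covariate named.

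Two other models carry more. The interim model is "A multivariable Bayesian prediction model that incorporates baseline characteristics and NFL levels pre-randomization and intermediate NFL levels ascertained at 12 weeks as covariates". The model under Dealing with missing outcome data, used when more than 10% of an arm lacks both the week 18 and week 24 values, also includes baseline characteristics. Neither place lists those characteristics.

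Section 11.1 then defers detail: "Further details of the primary outcome analysis will be pre-specified in the statistical analysis plan".

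**The concern.** When allocation is balanced on a factor that predicts the outcome, the balance already removes that factor's contribution from the difference between arms. If the model omits the factor, its variance stays in the residual, and the reported interval is wider than the estimate's true uncertainty. The usual practice is to analyse by the factors used to balance.

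The comparisons at stake are the pairwise ones. They use a 0.10 log10 margin and a 97.5% (or 2.5%) posterior threshold, and they feed the choice of reference drug and the ranking of Phase III candidates. As written, the same pairwise probabilities would come from a model with baseline NFL alone, or from one with unspecified baseline characteristics, depending on how much outcome data is missing.

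**Working it through.** **Inputs from the protocol (Section 11.2).** "The typical standard deviation at any given measurement time point was 0.35 log10 units"; futility calculations "assuming a correlation between baseline and follow-up of 0.80"; "the target sample size is set at 80 patients per candidate drug"; difference and margin 0.10 log10 units; threshold 97.5%, treated here as one-sided 0.025. The correlation of 0.80 is stated for the futility analyses and is assumed to carry over to the pairwise ones. The superiority check uses the Section 11.2 rule (any larger decrease).

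**Step 1: the plan's own figure, with baseline NFL alone.**
- Residual SD, change score: 0.35 × √(2 × (1 − 0.80)) = 0.221.
- Residual SD, baseline-adjusted: 0.35 × √(1 − 0.80²) = 0.210.
- SE of a difference at 80 per arm: SD × √(2/80), giving 0.0350 and 0.0332.
- Power = Φ(0.10/SE − 1.96): 81.5% (change score; 77 per arm needed for 80%) and 85.4% (baseline-adjusted; 70 per arm needed).

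The stated power of more than 80% is therefore reproduced without the minimisation factors. These figures use one baseline and one follow-up value. Averaging two of each under compound symmetry gives about 98%.

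**Step 2: interval width.** Let R² be the share of residual variance that onset and site group explain beyond baseline NFL. The protocol gives no value, so a range is assumed. Adjustment multiplies the half-width by √(1 − R²). With SD 0.210 the half-width without the factors is 1.96 × 0.0332 = 0.0651.

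| R² | √(1 − R²) | Half-width with factors | Narrowing | Power with factors |
|---|---|---|---|---|
| 0 | 1.000 | 0.0651 | 0% | 85.4% |
| 2% | 0.990 | 0.0644 | 1.0% | 86.0% |
| 5% | 0.975 | 0.0634 | 2.5% | 87.1% |
| 10% | 0.949 | 0.0617 | 5.1% | 88.8% |

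With the change-score SD of 0.221 the power column reads 81.5%, 82.3%, 83.4% and 85.4%.

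**Step 3: power lost by omission.** The fall down the power column overstates the loss, because minimisation already shrinks the true spread of the unadjusted estimate. At R² = 10% that spread is 0.0332 × 0.949 = 0.0315 while the reported half-width stays at 0.0651. Power without the factors is then Φ((0.10 − 0.0651)/0.0315) = Φ(1.11), or about 87%, against 88.8% with them: a loss of about 2 points.

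**Step 4: simulation.** 4,000 two-arm trials of 80 per arm were generated with minimisation on a two-level and a three-level factor. Assumed: biased-coin probability 0.8, factor shares 30/70 and 45/35/20, flat-prior linear model, 1:1 allocation, all patients eligible for both arms.

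| R² | Coverage of 95% interval, without / with factors | Power, without / with factors |
|---|---|---|
| 0 | 95.1% / 94.9% | 85.3% / 85.2% |
| 2% | 95.1% / 94.9% | 85.7% / 86.2% |
| 5% | 95.6% / 95.0% | 84.5% / 85.7% |
| 10% | 96.1% / 95.0% | 85.6% / 87.7% |

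Coverage without the factors never fell below the nominal level.

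**The case against.** The strongest objection is that this rests on silence. Section 11.1 does not say that baseline NFL is the sole covariate. It hands further detail to the statistical analysis plan, and the list of minimisation factors in a model is ordinary content for that document. This stands, and it rules out saying that the trial will in fact omit the factors. What remains is that the protocol gives wider covariates to the prediction models and none to the model behind the pairwise verdicts.

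It can also be said that baseline NFL may already carry most of the prognostic information. The protocol reports a correlation of at least 0.85 between repeated measures. R² could then be near zero and the gain with it. That stands too, and is why the range starts at zero.

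Three stronger readings are tempting and are not supported:

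- *The pairwise decisions lose their stated error control.* With patients eligible for both arms, omission widens intervals, so errors fall on the safe side. The protocol's thresholds are posterior probabilities, not frequentist error rates.
- *The interim and final models contradict each other.* The interim model predicts outcomes for patients with incomplete follow-up. It may properly use more covariates than a model for observed outcomes.
- *Arm-specific eligibility makes omission biasing.* Nifedipine excludes patients who cannot swallow and have no gastrostomy or equivalent, so minimisation cannot guarantee equal bulbar shares. But the documents give neither the resulting imbalance nor the effect of onset on NFL beyond baseline, and any bias is the product of the two. The simulation assumed common eligibility and does not test this. An onset term would remove that component if it exists, but would not restrict a comparison to patients eligible for both arms.

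**Conclusion.** The point holds as a minor one. As written, the protocol balances on two factors and does not name them in the model for the pairwise comparisons. Under common eligibility, leaving them out costs between nothing and about 5% in interval width, and 0 to 2 points of power, for an assumed R² of 0 to 10%. The direction is conservative, and the sample-size claim survives.

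The conclusion rests on the assumed R², on the 0.80 correlation applying to the pairwise analyses, and on a normal approximation to a model with minimally informative priors. It does not extend to futility, potential effectiveness or change from baseline, which are estimated within an arm and contain no between-arm contrast.

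**What to change.** Add one sentence to Section 11.1, and carry it into Dealing with missing outcome data: all pairwise NFL comparisons adjust for site of onset (bulbar, spinal) and site-volume group (high, medium, low) in addition to baseline NFL, whichever of the two models supplies the posterior. If the statistical analysis plan already says this, a cross-reference is enough.

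The cost is three parameters (one for onset, two for site group) with about 160 patients per comparison, using data the minimisation already requires. Because the cut-offs and analysis timing were set by simulation, a brief recheck of the operating characteristics with the added terms may be needed.
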